3.1. Inclusion criteria

- A diagnosis of AIDS according to the 1993 Centers for Disease Control and Prevention (CDC) definition (with or without clinical symptoms of CMV retinitis or other ocular complications of AIDS)
- Age 13 years or older
- Signed consent statement
- Patients with newly diagnosed (within 45 days of enrollment) Ocular Opportunistic Infections (OOIs)
- Patients without a newly diagnosed Ocular Opportunistic Infection (OOI) diagnosed with AIDS after 1 Jan 2001

3.2. Exclusion criteria

None.

3.3. Enrollment of patients with Ocular Opportunistic Infection (OOI)

As stated in section 3.1, patients with existing CMV retinitis or other ocular complications diagnosed on or after 1 Jan 2001 are eligible for enrollment. In order to have sufficient power to detect differences in visual outcomes or mortality associated with treatments or other factors in this group of patients, at least 300 patients will be enrolled. The maximum number of such patients to be enrolled will be 600.

3.4. Participation in other studies

Patients enrolled in LSOCA may be enrolled in other studies including treatment trials, and vice versa. Consolidation of study visits between LSOCA and other studies is encouraged when possible to avoid duplicate tests done on patients.

3.5. Monitoring

Characteristics of patients enrolled, such as the proportion of the cohort with prevalent CMV retinitis, will be monitored by the Coordinating Center and the SOCA Policy and Data Monitoring Board. If the characteristics of the patient population enrolled or the rate of enrollment are such as to jeopardize the goals of the study, the eligibility criteria and enrollment guidelines may be modified.

3.6. Consent

Once it has been determined that a patient is eligible for the study, the specifics of the study will be explained and discussed with the patient. Patients considering participating in the study will be given the consent statement and should be allowed sufficient time to decide whether to enroll. Patients 13-17 years old will be provided an Assent Statement, which should be reviewed and signed by both the patient and his/her parent or guardian. The Consent Statement should be reviewed and signed by the parent/guardian as well. It is important to give patients the time they need to ensure informed consent.

LSOCA Protocol Version 6.0

4. Data collection plan

All patients will be on a 6-month followup schedule. All followup visits will be clinic visits (Appendix 1A, page 26) with telephone contact in between clinic visits (Appendix 1B, page 27). Patients who enrolled in the study with No Ocular Opportunistic Infection (No OOI) and develop one during followup will be switched to the same data collection schedule as patients who enrolled with an Ocular Opportunistic Infection (OOI) (Appendix 1A, page 26). Data will be collected at every clinic visit, at the time of diagnosis of, an Ocular Opportunistic Infection (OOI) or at the time of death. These are data collection schedules, not patient care schedules. All patients will be followed until death or a common study closeout. Study closeout is expected to occur one year after enrollment of the last patient.

Data collection will include ophthalmologic examination, fundus photographs as appropriate, medical history, treatment history for AIDS and CMV diseases, and quality of life assessment. Laboratory studies and blood specimens for banking also will be obtained.

4.1. Telephone visits

Patients will be contacted by telephone or mail at the halfway point (3 months) between followup visits at the clinic to ascertain vital status and screen for eye conditions developed during the interval. These contacts are considered scheduled followup visits. Patients reporting eye problems will be scheduled for an eye examination by a study ophthalmologist.

4.2. Ophthalmologic evaluations

The recommended order for ophthalmologic procedures is as follows: assessment of best corrected visual acuity with refraction first, followed by assessment of contrast sensitivity, Humphrey field, Goldmann field, and then ophthalmologic exam and fundus photography.

Ophthalmologic examinations will be conducted at baseline, at the time of diagnosis of an Ocular Opportunistic Infection (OOI), and at every clinic followup visit. Examinations will include assessment of best corrected visual acuity with refraction, Pelli-Robson contrast sensitivity test, **biomicroscopy**, measurement of intraocular pressure (IOP), evaluation of pupils, assessment of motility and alignment, and dilated indirect ophthalmoscopy.

Visual field testing will be conducted using Humphrey field analyzer and Goldmann perimeter. Automated perimetry with the Humphrey field analyzer using the 24-2 program for threshold testing will be performed at baseline and annually on all patients, with or without an Ocular Opportunistic Infection (OOI). Humphrey field testing also will be conducted at the time of diagnosis of an Ocular

Opportunistic Infection (OOI).

Visual field with Goldmann perimeter will be performed only at baseline for patients without an Ocular Opportunistic Infection (OOI). For patients who enrolled in the study without an Ocular Opportunistic Infection (OOI) and develop one during followup, Goldmann field testing will be performed at the time of diagnosis of Ocular Opportunistic Infection (OOI), and at every followup visit thereafter. For patients who enrolled in the study with an Ocular Opportunistic Infection (OOI), Goldmann field testing will be performed at baseline, at the time of diagnosis of an Ocular Opportunistic Infection (OOI), and at every followup visit.

Procedures for visual acuity, refraction, and Goldmann visual fields are described in the SOCA General Handbook. Procedures for contrast sensitivity and automated perimetry are described in the LSOCA Handbook.

4.3. Fundus photography

Fundus photographs will be taken at baseline and every 5 years for patients without an Ocular Opportunistic Infection (OOI). If a patient has already completed a five year visit (e.g., Followup Visit 20), then the fundus photographs should be obtained at the next scheduled visit. For patients who enrolled in the study without an Ocular Opportunistic Infection (OOI) and develop one during followup, fundus photographs will be taken at the time of diagnosis of an Ocular Opportunistic Infection (OOI), and at every followup visit thereafter. For patients who enrolled in the study with an Ocular Opportunistic Infection (OOI), fundus photographs will be taken at baseline, at the time of diagnosis of an Ocular Opportunistic Infection (OOI), and at every followup visit.

Photographs will be taken as described in the Fundus Photograph Reading Center (FPRC) protocol located in the SOCA General Handbook.

4.4. Medical history

Medical history will be obtained via patient interview. Interviews will be conducted at baseline and at every clinic followup visit. Medical history will include ophthalmic history, health history, date of AIDS diagnosis, basis for AIDS diagnosis, occurrence of opportunistic infections and other manifestations of AIDS, and treatment history for HIV and CMV. ACTG diagnostic criteria and coding scheme will be used to define opportunistic infections (OI's). A questionnaire regarding symptoms of CMV disease will be administered as part of the medical history review. Information regarding the patient's insurance status, and changes in insurance status also will be collected.

4.5. Quality of life

Quality of life measures will be collected at baseline and at every clinic followup visit. A questionnaire will be used to collect information regarding health-related quality of life, a subjective assessment of vision and overall quality of life (utility). It is recommended that the quality of life questionnaire be administered at the beginning of the visit to avoid events during the visit from influencing responses to the questionnaire.

4.6. Laboratory studies

Laboratory studies will be conducted at baseline and at every clinic followup visit. Laboratory data collected in the context of another study may be used for LSOCA if the data were collected within the visit time window.

Laboratory studies will include hematology serum chemistry and lymphocyte subset analysis for all patients. The amount of blood for hematology, serum chemistry, and lymphocyte subset analysis is restricted to no more than a total of 17 mL per draw. Data existing on HIV viral load analysis at the clinic will be collected. If HIV data are not available from medical records within the visit time window, blood should be collected for local HIV viral load determination.

4.7. Specimen banking

Plasma and leukocytes will be collected for banking at baseline and at every clinic followup visit. Blood (15 mL) will be collected into two 8.5 mL yellow-top ACD tubes and processed locally to obtain aliquots of plasma and 5×10^6 cell aliquots for banking. Procedures for collection and shipment of blood specimens for banking are described in the LSOCA Handbook. Other virologic and immunologic measurements will be made based on the advice of the SOCA Study Officers and other experts.

4.8. Interim visits

Patients will be instructed to notify the clinic and schedule a clinic visit whenever they experience a problem with their eyes or vision or are informed of a diagnosis of an Ocular Opportunistic Infection (OOI). If a study visit at the clinic for that visit window has already occurred, such a visit will be deemed an "interim visit." Data will be collected at an interim visit only if the patient is diagnosed with an Ocular Opportunistic Infection (OOI). Data to be collected at an interim visit include eye history, eye examination, visual acuity, contrast sensitivity, Humphrey and Goldmann visual field, contrast sensitivity, and fundus photography.

If the patient is diagnosed with an Ocular Opportunistic Infection (OOI) at a clinic visit that is not an interim visit, all evaluations and procedures for an Ocular Opportunistic Infection (OOI) for that visit will be performed. Patients diagnosed with an Ocular Opportunistic Infection (OOI) either at an interim visit or at a scheduled followup visit will be seen at the clinic for all subsequent followup visits.

4.9. Missed visits

Patients will be contacted by phone for missed visits to ascertain vital status, to obtain information on eye problems, and to conduct quality of life assessment.

LSOCA Protocol Version 6.0

5. Outcome measures

The outcomes of primary interest are incidence of CMV retinitis, incidence of other ocular complications, and mortality. Additional outcomes of interest include incidence of sequelae of AIDS-related eye disease (e.g., rhegmatogenous retinal detachment, macular edema), incidence of complications of treatment, visual function and quality of life.

5.1. Incidence of AIDS-related eye diseases and ocular complications

Incidence of CMV retinitis and other AIDS-related eye diseases and ocular complications, such as retinal detachments, will be defined as the number of newly diagnosed cases out of the total number of person-years of followup at risk from patients without the complication of interest. Methods to estimate net incidence and time with CMV retinitis will take into account patients' high risk for death.

Data will be collected on the incidence and characteristics of ocular complications that are a direct result of HIV disease, opportunistic infections, or a complication of ocular disease or their treatment. Definitions of ocular complications are provided in Appendix 2 (page 28).

5.1.1. Ocular Opportunistic Infection (OOI) ~~Major ocular complications~~

For purposes of LSOCA, major ocular complications are defined as those that are chronic and place a patient at significant risk for prolonged or permanent vision loss. These include:

- CMV retinitis,
- Herpetic retinitis,
- Toxoplasmic retinitis,
- Cryptococcal choroidopathy,
- Pneumocystic choroidopathy,

5.1.2. No Ocular Opportunistic Infection (OOI)

Other ocular complications of interest include: large vessel vaso-occlusive disease, and optic nerve abnormalities: papilledema, optic nerve disease associated with cryptococcal meningitis, or other serious optic neuropathy, HIV retinopathy, syphilitic retinitis, macular edema, epiretinal membrane, cranial nerve lesions, keratitis/conjunctivitis, Kaposi's sarcoma of the ocular adnexae, lymphoma, molluscum contagiosum, cataract, and complications of infections or their treatment such as retinal detachment, uveitis, and hypotony.

5.2. Mortality

Time to death will be measured from the date of enrollment to date of death and will be censored at study closeout for patients still living.

5.3. Visual function

Outcome measures for visual function in patients with AIDS-related eye diseases will include change in best corrected visual acuity from baseline, incidence of significant vision loss (e.g., < 20/200), change in visual field from baseline, and change in contrast sensitivity from baseline.

5.3.1. Visual acuity

Best corrected visual acuity will be measured using logarithmic visual acuity charts according to the protocol developed for the Early Treatment Diabetic Retinopathy Study (ETDRS)¹⁰. Visual acuity will be expressed as the number of letters read correctly (visual acuity score). Change in visual acuity will be expressed as the decrease in the number of total letters read in best corrected vision from baseline or from the time of diagnosis for patients without AIDS-related eye diseases at enrollment. Visual acuity events will be defined as loss of 15 letters of vision, a doubling of the visual angle, or visual acuity 20/200 or worse.

5.3.2. Contrast sensitivity

Contrast sensitivity will be measured with the Pelli-Robson chart. The threshold contrast sensitivity value (the lowest contrast level at which at least 2 of the 3 letters were reported correctly),³¹ as well as the "by-letter" contrast sensitivity score (giving credit for each individual letter read correctly)⁷ will be used to assess change in contrast sensitivity and rate of change over time.

5.3.3. Visual field

Visual field with Goldmann perimeter will be measured using the Diabetic Retinopathy Study visual field protocol⁵. A visual field score is computed by summing the degrees of field along 12 meridians. Change in visual field will be expressed as the decrease in the number of total degrees of field from baseline or from the time of diagnosis for patients without AIDS-related eye diseases at enrollment. Rate of visual field loss per month also will be evaluated.

Visual field with Humphrey field analyzer using the 24-2 program for threshold testing will be measured according to the Humphrey Field Analyzer User's Guide⁴. Patient reliability will be assessed by fixation losses, false-negative responses, and false-positive responses. Four global indices: mean deviation (MD), pattern standard deviation (PSD), short-term fluctuation (SF) and corrected pattern standard deviation (CPSD), which summarize the point-by-point field data into single numbers will be used to assess deficits and intra-test reliability. Field change and rate of

change will be evaluated. Additionally, the glaucoma hemifield test (GHT) will be used to assess for asymmetric visual thresholds. The proportion of patients with normal, borderline, and abnormal GHT will be estimated.

5.4. Quality of life

A questionnaire will be used to measure health status and subjective visual function. The questionnaire includes the SOCA vision-related instrument⁴³, the Medical Outcome Study Short-form General Health (MOS-HIV) Survey⁴⁴, and the EuroQoL⁹. The vision-related instrument and the MOS-HIV will provide data on self-evaluated ability to see, ability to perform functions of daily life, and overall health status. The EuroQoL provides utility scores which allow estimation of quality-adjusted life years. Quality-adjusted life years incorporate both quality and length of survival time into a single measure^{13,15,39}. These data will be used separately and in combination to evaluate visual function and its relationship to overall quality of life.

5.5. Other morbidity

The incidence of extraocular CMV disease and other opportunistic infections will be compared among subgroups of patients. ACTG diagnosis codes will be used to define opportunistic infections.

LSOCA Protocol Version 6.0

6. Biostatistics

6.1. Data analysis

Secular trends in the rates of ocular complications of AIDS will be examined by observing changes in annual incidence in the longitudinally followed cohort. These trends also will be evaluated among subgroups of patients. Incidence will be defined as the number of newly diagnosed cases of specific ocular complications out of the total number of person-years of followup from patients without the complication in question. In addition, methods to estimate net incidence and time with CMV retinitis in patients at high risk for death will be employed. These methods allow for the incorporation of death as a censoring event but do not require the usual assumption of an equivalent experience among censored individuals as those who remain under followup¹⁸. Estimates of probabilities of events are usually lower using these methods because once patients are censored due to death they are not assumed to have any events.

Relationships between clinical course of ocular complications of AIDS and treatment strategies will be examined. Comparisons of disease progression, visual outcomes, and survival among subgroups of patients defined by demographic and clinical characteristics and by treatment history will be conducted adjusting for potential confounders with proportional hazards regression techniques. Of particular interest are the long-term effects associated with discontinuation of secondary prophylaxis (maintenance therapy) among patients with CMV retinitis who respond to HAART. For this analysis, HAART response will be explored in terms of an increase in CD4+ T cell counts and/or a decrease in HIV RNA viral load. Since a major risk factor identified for CMV retinitis is low CD4+ T cell counts^{19,21,36}, we will explore using change in CD4+ T cell counts as one way to gauge HAART response. For example, HAART response may be defined as an increase in CD4+ T cell counts from ≤ 50 cells/ μ L to ≥ 100 cells/ μ L. The duration of HAART use, time of first use, and use of HAART as a time-dependent covariate also will be explored.

The effect of HAART response and other factors on the incidence of ocular complications of AIDS, particularly CMV retinitis, will be addressed by estimating the relative risk of ocular complications among different subgroups. Baseline and time-dependent risk factors for development of ocular complications, including demographic characteristics, HIV treatment, CMV prophylaxis, HIV and CMV viral load, and CD4+ T cell counts (current and nadir levels), will be explored using Cox regression models for incident and recurrent CMV retinitis and other ocular complications^{25,26}. Predictive models estimating risk of developing CMV retinitis and other ocular complications will be explored using logistic regression and parametric survival models such as lognormal and Weibull. The interrelationship of HIV viral load, CMV viral load, and CD4+ T cell counts over time will be explored. The bidirectional effect of HIV load on CMV disease and CMV viremia also will be explored.

Use of HIV viral load has proved to be an important tool for management of HIV-infected patients. Similarly, the measurement of CMV viral load along with CD4+ T cell counts is likely to improve our ability to identify patients at high risk of CMV retinitis, which currently is based only on CD4+ T cell counts. Even if the use of both tests together proves no better than the use of either test alone at identifying populations at high risk for CMV disease, it will still be important to determine an optimal algorithm for the clinical use of these tests.

The results of these analyses will be used to identify populations at high risk for ocular complications, who might be targeted for screening or primary prophylaxis.

6.2. Sample size consideration

We anticipate enrolling a cohort of 2,800 patients with AIDS for additional followup. At least 300 patients but no more than 600 patients with existing CMV retinitis will be enrolled. The overall sample size and the minimum and maximum number of patients enrolled with existing CMV retinitis are determined based on the ability to meet study objectives and on the basis of resource availability.

Data analysis for LSOCA will be largely exploratory, ie, hypothesis generating, rather than hypothesis testing. However, the planned sample has sufficient power to test certain specific hypotheses, eg, response to HAART therapy and the development of CMV retinitis. It is large enough to detect reasonable relative risks (ie, a relative risk of 2) for other unspecified hypotheses, even for rare events.

Table 1. Minimum detectable relative risk* of development of CMV retinitis

CMV retinitis rate [†] in HAART responders	% with nadir CD4 \leq 50 cells/ μ L	
	50%	30%
2.5%	1.98	2.32
5%	1.68	1.91
10%	1.48	1.64
15%	1.40	1.53

*Specifications for calculations: total number of patients enrolled free of CMV retinitis = 1,400; type I error = 0.05; power = 80%; exponential survival function and proportional hazards; accrual = 4 years; followup after sample size is achieved = 1 year; loss to followup = 10%; and proportion respond to HAART = 50%.

[†]Annual rate in patients with nadir CD4+ T cell counts \leq 50 cells/ μ L who respond to HAART.

Table 1 provides estimates of the minimum detectable relative risk of developing CMV retinitis in patients with a nadir CD4+ T cell counts ≤ 50 cells/ μL in relation to HAART response if 1,400 patients initially free of CMV retinitis are enrolled in the study, assuming that 50% of the patients are HAART responders (the hypothesized proportion of patients who respond to HAART therapy has little effect on these estimates). Each row corresponds to a hypothesized CMV retinitis rate among patients initially free of CMV retinitis who respond to HAART; each column corresponds to a hypothesized proportion of patients enrolled with a nadir CD4+ T-cell counts ≤ 50 cells/ μL . (A review of medical records for a subset of AIDS patients seen at the Johns Hopkins SOCA clinical center in the first 6 months of 1997 revealed that about 50% of the patients seen had a nadir CD4+ T cell count ≤ 50 cells/ μL .) Because some patients with a nadir CD4+ T cell count > 50 cells/ μL at enrollment will move into a higher risk group during followup, an even smaller relative risk may be detected. However, the clinical course for these patients on HAART therapy cannot be anticipated at this time. In addition, these calculations are based on patients with nadir CD4+ T cell counts ≤ 50 cells/ μL only. Patients with CD4+ T cell counts > 50 cells/ μL have a lesser, but real, risk of CMV retinitis. When these patients are included in the calculations, the detectable relative risks are smaller than those presented in the table.

The study needs to enroll a minimum sample size of 300 patients with existing CMV retinitis to allow detection of a relative risk (RR) of 2 for pairwise comparisons among three equally sized risk groups (eg, by treatment regimen or viral load) if the one-year event rate (eg, vision loss or mortality) in the referent (low risk) group is 10%. A larger sample size is needed if the event rate is less than 10%.

Table 2. Minimum detectable relative risk for vision loss greater than three lines in patients with CMV retinitis*

Rate [†] of vision loss > 3 lines in the referent group	Sample size	
	300	600
5%	2.40	1.93
10%	1.99	1.66
15%	1.82	1.55
20%	1.72	1.48

*Specifications for calculations: type I error = 0.05; power = 80%; exponential survival function and proportional hazards; accrual = 4 years; followup after sample size is achieved = 1 year; loss to followup = 10%; three equally sized groups.

[†]Annual rate in patients with CMV retinitis in the referent group.

Table 2 provides estimates of the minimum detectable relative risk for vision loss greater than three lines in patients with CMV retinitis. Each row corresponds to a hypothesized proportion of patients with vision loss greater than three lines in one year in the referent group (In the Monoclonal Antibody Cytomegalovirus Retinitis Trial, about 50% of the patients had vision loss greater than three lines at one year); each column corresponds to the proposed minimum and maximum number (the maximum number is limited by the number of patients enrolled free of CMV retinitis and the total resource availability) of patients enrolled with existing CMV retinitis. These estimates are conservative as patients who develop CMV retinitis during followup also will be included in the analysis.

The Coordinating Center and the SOCA Policy and Data Monitoring Board will review event rates and patient characteristics (eg, proportion of patients with a nadir CD4+ T cell counts ≤ 50 , proportion of patients respond to HAART) periodically. The proposed sample size will be adjusted as necessary to maintain adequate power for analysis.

LSOCA Protocol Version 6.0**7. Rights and responsibilities**

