Ocular complications other than HIV retinopathy and CMV retinitis occur less frequently. Ocular toxoplasmosis, herpes zoster retinitis, and pneumocystis choroidopathy have been reported to occur in less than 1% of patients²¹. A rapidly progressing form of herpes zoster retinitis that responds poorly to treatment also has been reported in patients with AIDS^{8,23,27,30}. The frequency of these infections, like that of CMV retinitis, has changed over the course of the AIDS epidemic. For example, the incidence of pneumocystis choroidopathy increased with the use of aerosolized pentamidine for PCP prophylaxis but decreased with the use of systemic prophylaxis with trimethoprim-sulfamethoxazole (TMP-SMX). The incidence of ocular toxoplasmosis also seems to have decreased with systemic PCP prophylaxis with TMP-SMX.

A survey of the number of HIV-positive patients followed or screened for ocular complications during the first 6 months of 1997 at SOCA clinical centers was conducted. During the 6-month period, 4,292 patients with HIV were screened. Of the screened patients, 83% were male, 58% were

white, 73% were bisexual or homosexual, and 41% had CD4+ T cell counts 100 cells/ μ L or less. Extrapolating from the survey, the estimated annual total number of patients screened at 19 SOCA clinics is 8,584 with 724 newly diagnosed cases of ocular complications (excluding HIV retinopathy) and 1,398 prevalent cases of ocular complications (excluding HIV retinopathy). Among the newly diagnosed patients, 52% had CMV retinitis, 18% had neuro-ophthalmic lesions, 7% had herpes zoster ophthalmicus, 10% had drug-induced lesions, and 13% had other types of complications (excluding HIV retinopathy). The distribution of complications for prevalent patients – HIV patients with diagnosed ocular complications – was: 83% CMV retinitis, 5% neuro-ophthalmic lesions, 4% herpes zoster ophthalmicus, 2% drug-induced lesions, and 6% other types of complications (excluding HIV retinopathy). These results indicate that CMV retinitis remains the major ocular complication of AIDS even in the era of HAART.

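### Section 6.2 claims power to detect a relative risk of 2 even when events are rare; under the protocol's own assumptions this fails below about 0.6% per year, even with all 2,800 patients

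*Protocol*

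**What the plan says.** Section 6.2 describes the analysis as mainly exploratory, then makes an exception for power. The sample is said to suffice for certain specific hypotheses, and beyond those: "It is large enough to detect reasonable relative risks (ie, a relative risk of 2) for other unspecified hypotheses, even for rare events". The sentence does not define rare and does not say which patients or what exposure split it has in mind.

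Two tables of minimum detectable relative risk follow. Both specify "type I error = 0.05; power = 80%; exponential survival function and proportional hazards", with 4 years of accrual, 1 further year of follow-up and 10% loss.

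- **Table 1** concerns CMV retinitis. It starts from "total number of patients enrolled free of CMV retinitis = 1,400" and uses only the 50% or 30% of them with nadir CD4+ count at or below 50, half being HAART responders. Its lowest rate is 2.5% per year, where the detectable relative risk is 1.98 (50% column) or 2.32 (30% column).
- **Table 2** concerns vision loss in 300 or 600 patients with CMV retinitis, for "pairwise comparisons among three equally sized risk groups". Its lowest rate is 5% per year, with 2.40 (300 patients) or 1.93 (600).

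For the 300-patient minimum, the text adds: "A larger sample size is needed if the event rate is less than 10" percent. Section 1.1 says of several other complications: "Ocular toxoplasmosis, herpes zoster retinitis, and pneumocystis choroidopathy have been reported to occur in less than 1% of patients".

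**The concern.** The sentence is an unqualified statement of power, and nothing in the section supports it for rare events: no table row lies below 2.5% per year. Incidence of other ocular complications is an outcome of primary interest (section 5). Section 5.1.1 lists herpetic retinitis, toxoplasmic retinitis and pneumocystic choroidopathy individually, and section 6.1 plans Cox models for ocular complications, with the results used to identify populations for screening or primary prophylaxis. If the sentence is wrong, the protocol credits the study with a sensitivity that it lacks for individual rare diagnoses.

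**Working it through.** **Inputs.** From section 6.2: type I error 0.05, power 80%, exponential survival, accrual A = 4 years, further follow-up F = 1 year, loss 10%. Cohort 2,800, of whom 300 to 600 have CMV retinitis at entry, so 2,200 to 2,500 are free of it. Table 1 uses 1,400. My assumptions: two-sided test (one-sided variants fit the tables worse), uniform accrual, loss applied as 0.9 × N.

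**Formulas.** With exposed fraction p and relative risk RR:

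- Events needed: d = (1.960 + 0.8416)² / [p(1−p)(ln RR)²]
- Hazard: h = −ln(1 − annual rate)
- Probability of an event: P(h) = 1 − [exp(−hF) − exp(−h(A+F))] / (hA)
- Events expected: 0.9 N [(1−p)P(h) + p P(RR·h)]
- Power: Φ(√(d p(1−p)) · ln RR − 1.960), with d the events expected

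**Reproducing the tables.** Table 1 has N = 700 or 420, p = 0.5. Table 2 compares two thirds of 300 or 600, p = 0.5.

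| Table 1 rate | Stated (50% / 30%) | Recomputed |
|---|---|---|
| 2.5% | 1.98 / 2.32 | 1.99 / 2.33 |
| 5% | 1.68 / 1.91 | 1.69 / 1.92 |
| 10% | 1.48 / 1.64 | 1.49 / 1.65 |
| 15% | 1.40 / 1.53 | 1.41 / 1.54 |

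| Table 2 rate | Stated (300 / 600) | Recomputed |
|---|---|---|
| 5% | 2.40 / 1.93 | 2.42 / 1.94 |
| 10% | 1.99 / 1.66 | 2.01 / 1.67 |
| 15% | 1.82 / 1.55 | 1.84 / 1.56 |
| 20% | 1.72 / 1.48 | 1.74 / 1.50 |

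All 16 cells agree within about 0.02, so the method matches the protocol's.

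**Events needed for RR 2.** (2.8016)² = 7.849 and (ln 2)² = 0.4805.

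- Equal groups: 7.849 / (0.25 × 0.4805) = 65.3, so 66.
- One fifth exposed: 7.849 / (0.16 × 0.4805) = 102.1, so about 102.

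**Lowest referent rate giving 80% power for RR 2 (4 + 1 years).**

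| Patients at risk | Equal groups | One fifth exposed |
|---|---|---|
| 1,400 | 1.19%/yr | 2.35%/yr |
| 2,200 | 0.75%/yr | 1.47%/yr |
| 2,500 | 0.66%/yr | 1.29%/yr |
| 2,800 | 0.58%/yr | 1.15%/yr |

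**Power for RR 2 with all 2,800 patients, equal groups.** The protocol states no rate below 2.5% in its tables, so these rates are assumptions shown as a range.

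| Referent rate | Events expected | Power | Detectable RR |
|---|---|---|---|
| 1%/yr | 111 | 95% | 1.7 |
| 0.5%/yr | 56 | 74% | 2.1 |
| 0.25%/yr | 28 | 45% | 2.6 |
| 0.1%/yr | 11 | 21% | 3.8 |

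For the last row: h = 0.0010005, P(h) = 0.002996, P(2h) = 0.005982; events = 0.9 × 2,800 × 0.004489 = 11.3; power = Φ(√(11.3 × 0.25) × 0.6931 − 1.960) = Φ(−0.79) = 0.21.

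**Illustration from section 1.1.** Assume that exactly 1% of 2,800 patients had one of the complications reported there in less than 1%. That is 28 events. Power with equal groups = Φ(√7 × 0.6931 − 1.960) = 0.45; detectable RR = exp(2.8016 / √7) = 2.9. With one fifth exposed, power is 31%.

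**Longer follow-up.** With an assumed 10 years' accrual plus 1 year, the 2,800-patient threshold at equal groups falls to about 0.29%/yr, and power at 0.1%/yr is 38%.

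**The case against.** Several points on the other side stand.

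- **Subset figures.** A reader might infer from the cells above 2, and from the remark about rates under 10%, that the protocol's tables refute the claim for the whole cohort. They do not. The 2.32 is for 30% of 1,400 (420 patients with low nadir counts), the 2.40 is for 100 against 100 patients with CMV retinitis, and the remark concerns those same 300 patients. Section 6.2 also says that including patients with higher counts lowers the detectable relative risk, and calls Table 2 conservative. These figures show the claim failing for those subsets only.
- **Uncommon but not rare.** With a balanced exposure the whole cohort reaches RR 2 at about 0.6 to 0.75% per year. The sentence is therefore not false throughout.
- **The combined outcome.** It would be wrong to conclude that other ocular complications taken together are out of reach. The survey in section 1.1 extrapolates to 724 new cases per 8,584 patients screened, 48% of them not CMV retinitis: 724 × 0.48 / 8,584 is roughly 4% a year. Neuro-ophthalmic lesions (18%) come to roughly 1.5%. These are HIV-positive clinic patients, so the figures are only indicative. The shortfall concerns individual rare diagnoses.
- **The 28 events.** Section 1.1 reports a frequency with no time base, from an earlier source. Applying it to 2,800 patients is an assumption, not a protocol figure.
- **Consequences.** A reader might infer that null results will be taken as evidence of no association. No passage plans that; the analysis is labelled largely exploratory, and event rates are to be reviewed and the sample size adjusted.

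None of this rescues the sentence. It is framed as an exception to the exploratory label. It covers unspecified hypotheses, so an even split cannot be presumed. A later review of event rates does not make a present claim of power true.

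**Conclusion.** The claim is wrong as written for rare events. Under the tables' own assumptions, an 80% chance of detecting a relative risk of 2 needs about 66 events with equal groups or about 102 with one fifth exposed. With all 2,800 patients, this corresponds to about 0.58% or 1.15% per year. At an assumed 0.1% per year, power is about 21% over 4 + 1 years and 38% over an assumed 10 + 1. The thresholds rest on a two-sided test, uniform accrual and loss taken as 0.9 × N, and on the reproduction of all 16 table cells. This is an overstated sentence about power. The tables are arithmetically sound, and no analysis or enrolment target is shown to depend on the sentence.

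**What to change.** In section 6.2, delete the closing words about rare events, or replace them with the bound. For example: *A relative risk of 2 is detectable with 80% power for outcomes with about 66 events when two groups are equal, or about 102 when one fifth of patients are exposed.* An equivalent statement as the lowest annual rate, for a named number at risk and exposure split, would serve as well. Optionally, add lower-rate rows (for example 0.1%, 0.5% and 1% per year) calculated on the whole cohort free of CMV retinitis, labelled as such so that they are not read against the subset columns. How sparse outcomes are to be reported can be left to the statistical analysis plan. The change is to text, with a few table rows if wanted. The design is unaffected, and the only cost is a less favourable stated figure.
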